#### 9.2.2 Secondary Efficacy Endpoints

Further efficacy of DZD will be evaluated by assessment of:

- Proportion of patients who suffer relapse, defined as recurrent disease caused by a strain identical to the baseline isolate, within 12 months post randomisation, out of patients completing 16 weeks of therapy and achieving stable culture conversion to negative (SCC) as defined below by week 08, with no positives to follow by the week 16 visit.
- Time to recurrent TB, and to relapse, within 12 months post randomisation
- Time to stable sputum culture conversion (SCC) to negative on liquid media (defined as two negative cultures without an intervening positive culture). Time will be measured as time on treatment until the first negative culture.
- Proportion of participants who achieved SCC at each time point during treatment
- Proportion of participants with negative sputum culture on solid media at WK 08 and other timepoints
- Proportion of participants developing drug resistance among those not converting to negative culture

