# 12.4 Treatment after End of Study Therapy (Post-study Access to Treatment)

The strategy recommended for participants to continue their TB treatment within the government health system is informed by two previous phase 2b TB trials with a 2-month experimental treatment, and the solution found for patients in Tanzania in collaboration with the national TB program in those past trials [27, 56, 59].

Patients who achieve two successive negative liquid media cultures, with no positives to follow by WK16 visit, the first of which is at or before WK 08, will NOT receive standard of care TB-treatment according to national guidelines as continuation phase to complete 6 months of treatment. Their planned post-treatment follow-up visits at WK 18, WK26, WK38 and WK52 will serve to determine

whether they have achieved lasting cure. Patients who will NOT fulfil at least one of these criteria will receive standard of care TB-treatment according to national guidelines until WK26 at a government health facility (continuation Phase).

They will be invited to return to the WK52 follow-up visit to determine their wellbeing and treatment outcome.

The review of culture results, and decision to discontinue or continue treatment will be made on the day before the WK16 visit. Should sufficient culture results to take this decision not be available by this timepoint, but available culture results indicate good response to treatment in the view of the investigator, this decision, and the start of continuation phase treatment, may be delayed until latest to WK16 (day112) + 6 days.

Should positive results become available after a decision is taken to discontinue treatment after WK16, the investigator should discuss these with the sponsor medical expert to come to a conclusion of whether the management of the patient should be changed, which should be done only in exceptions.

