11.3. Time to recurrent TB and relapse

Time to recurrent TB will be defined as time from randomization to first culture positive timepoint that leads to a classification of relapse or reinfection. Participants without reinfection or relapse will be censored at time of last culture result. Time to relapse will be defined in the same way, except considering only relapses (and not reinfections) as events.

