11.4. Time to culture conversion to negative on liquid media

Participants will be classified as having culture conversion to negative in liquid media if there are two consecutive culture negative timepoints without an intervening culture positive timepoint. Any other results will be ignored for the calculation of time to culture conversion. Culture timepoints will be classified as negative or positive according to the trial definition under 11.1.

Time will be taken from the date of randomization to the first occurrence of two consecutive negative culture timepoints.

Culture positive timepoints that occur after culture conversion has been achieved do not affect time to culture conversion.

This will be the primary definition of time to culture conversion. Primary analysis will be performed based on the primary definition. We will, in addition, perform two sensitivity analyses with alternative definitions of time to culture conversion:

- 1) The definition will be as above, with the exception that culture conversion can only be achieved if the two consecutive visits assessed as culture negative timepoints without an intervening culture positive timepoint are at least 28 days apart.
- 2) The definition will be as above, with the exception that culture conversion is only achieved provided no further culture positive timepoints occur after 'culture conversion', in the period up to and including the week 16 visits (a subsequent culture positive timepoint effectively 'cancels' out culture conversion).

12. Analysis Method

12.1. Analysis of time to culture conversion by dose group.

Descriptive summary statistics, such as mean/median of the time to culture conversion will be tabulated. Proportion of participants achieving culture conversion at each time point during treatment will be summarized using the Kaplan-Meier estimator with 95% confidence intervals.

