A Cox regression model will be used to compare each arm with different DZD doses to the background regimen without DZD, in time to culture conversion. The analysis will be adjusted for the baseline cultures using time to positivity (TTP) at the time of screening and enrolment. Demographic and clinical characters, such as gender, age, race, BMI, HIV status, smoking, alcohol usage, will also be adjusted in sensitivity analyses. To check the Proportional Hazard (PH) assumption, we will do statistical tests and graphical diagnostics based on the Schoenfeld residuals. ¹² If the PH assumption is violated, cox regression models will be presented but interpretation will take into account this violation and alternative methods will be added including restricted mean survival time ¹³.

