Table 2.2 Summary of Culture Results by Randomized Treatment of Week 02.

{Similar shell table as Table 2.1}

Table 2.3 Summary of Culture Results by Randomized Treatment of Week 08.

{Similar shell table as Table 2.1}

Table 2.4 Summary of Culture Results by Randomized Treatment of Week 12.

{Similar shell table as Table 2.1}

Table 2.5 Summary of Culture Results by Randomized Treatment of Week 14.

{Similar shell table as Table 2.1}

Table 2.6 Summary of Culture Results by Randomized Treatment of Week 16.

{Similar shell table as Table 2.1}

Table 2.7 Summary of Time to Positivity (TTP) by Treatment Arm of Week 00*.

TTP	Arm 1 D0 (N=x) n (%)	Arm 2 D400 (N=x) n (%)	Arm 3 D800-OD (N=x) n (%)	Arm 4 D1200 (N=x) n (%)	Arm 5 D800-BD (N=x) n (%)	Total (N=x) n (%)
Mean (SD)	xx	xx	xx	xx	xx	xx
Median	xx	xx	xx	xx	xx	xx
Min – Max	(xx, xx)	(xx, xx)	(xx, xx)	(xx, xx)	(xx, xx)	(xx, xx)

^{*}Same tables will be applied to each week (from week 00 to week 16).

Table 2.8 Analysis of Time to Culture Conversion on Liquid Media.

TTP	Arm 1 D0 (N=x) n (%)	Arm 2 D400 (N=x) n (%)	Arm 3 D800-OD (N=x) n (%)	Arm 4 D1200 (N=x) n (%)	Arm 5 D800-BD (N=x) n (%)
25th centile, weeks	xx	xx	xx	xx	xx
Median (50th centile), weeks	xx	xx	xx	xx	xx
75th centile, weeks	xx	xx	xx	xx	xx
Mean	xx	xx	xx	xx	xx

v1.0, February 13, 2023

% With culture conversion at 0 week					
% With culture conversion at 2 weeks	xx.x%	xx.x%	xx.x%	xx.x%	xx.x%
% With culture conversion at 4 weeks	xx.x%	xx.x%	xx.x%	xx.x%	xx.x%
% With culture conversion at 6 weeks	xx.x%	xx.x%	xx.x%	xx.x%	xx.x%
% With culture conversion at 8 weeks	xx.x%	xx.x%	xx.x%	xx.x%	xx.x%
% With culture conversion at 12 weeks	xx.x%	xx.x%	xx.x%	xx.x%	xx.x%
% With culture conversion at 14 weeks	xx.x%	xx.x%	xx.x%	xx.x%	xx.x%
% With culture conversion at 16 weeks	xx.x%	xx.x%	xx.x%	xx.x%	xx.x%
Unadjusted Hazard Ratio (95% CI)	1	xx(xx, xx)	xx(xx, xx)	xx(xx, xx)	xx(xx, xx)
Adjusted Hazard Ratio (95% CI)*	1	xx(xx, xx)	xx(xx, xx)	xx(xx, xx)	xx(xx, xx)

^{*} Analysis has been adjusted for: gender, age, race, BMI, HIV status, baseline culture (using time to positivity)

Table 2.9 Analysis of Time to Culture Conversion on Solid Media.

TTP	Arm 1 D0 (N=x) n (%)	Arm 2 D400 (N=x) n (%)	Arm 3 D800-OD (N=x) n (%)	Arm 4 D1200 (N=x) n (%)	Arm 5 D800-BD (N=x) n (%)
25th centile	xx	xx	xx	xx	xx
Median (50th centile)	xx	xx	xx	xx	xx
75th centile	xx	xx	xx	xx	xx
% With culture conversion at 0 week	xx.x%	xx.x%	xx.x%	xx.x%	xx.x%

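### SAP 11.4 and 12.1 set no end of observation for time to culture conversion, so conversions reached on non-study therapy after week 16 can enter the Cox hazard ratio

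*SAP*

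**What the plan says.** Protocol 9.2.2, on time to stable conversion in liquid media: "Time will be measured as time on treatment until the first negative culture".

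SAP 11.4, on the same endpoint: "Time will be taken from the date of randomization to the first occurrence of two consecutive negative culture timepoints". The title of SAP Figure 2.1 indicates that the event date is the first negative of the pair. The section gives no last eligible visit and no censoring date. Week 16 appears only in sensitivity definition 2, where "in the period up to and including the week 16 visits" limits which later positives cancel a conversion, not when a conversion may occur.

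SAP 12.1 on the analysis: "Proportion of participants achieving culture conversion at each time point during treatment will be summarized using the Kaplan-Meier estimator". Then: "A Cox regression model will be used to compare each arm with different DZD doses to the background regimen without DZD", with no time limit. Restricted mean survival time is the fallback if proportional hazards fails, with no truncation time. In the Table 2.8 shell the last percentage row is "With culture conversion at 16 weeks". The centile, mean and hazard-ratio rows carry no limit.

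The SAP does set such rules elsewhere. Section 11.3, on recurrence: "Participants without reinfection or relapse will be censored at time of last culture result". Section 10 drops time-to-positivity data collected after premature discontinuation.

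On treatment after week 16, Protocol 12.4 says that those who do not qualify to stop "will receive standard of care TB-treatment according to national guidelines until WK26 at a government health facility". Footnote A of the Schedule of Events removes FU2 and FU3 for them and keeps FU4 for everyone. Protocol 10.5.3 gives FU1 to all, and Protocol 11.2 has MGIT culture at FU1 to FU4.

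**The concern.** The protocol ties the endpoint to study treatment. The SAP rule, followed literally, runs for as long as cultures are taken, and those continue to WK52 in participants who have left the study regimen. Negatives obtained on national-programme drugs can therefore count as conversions in a comparison meant to describe delpazolid dose.

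The hazard ratios against D0 are at stake, together with the mean and any centile reached after week 16. If therapy after week 16 works about equally well in all arms, late events carry no dose contrast and dilute the one seen on treatment. With 15 participants per arm, one or two such events are visible in the result. The estimate could also depend on which database lock is used.

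**Working it through.** **1. Can such an event occur?** Take a participant positive at WK16. The next scheduled cultures are WK18 (Day 126) and, because FU2 and FU3 are omitted, WK52 (Day 364). If both are negative, they are two consecutive negative timepoints with no positive between them, and SAP 11.4 dates the conversion at about Day 126. Participants who converted between WK08 and WK16 are also referred onward, but they already have their event. A WK16 negative confirmed at WK18 has its first negative on study treatment.

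**2. Does a sensitivity definition remove it?** Definition 1 asks for at least 28 days between the negatives; 364 - 126 = 238 days, so the pair passes. Definition 2 cancels conversions followed by a positive up to week 16; this pair starts later, so it also passes.

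**3. Does the lock matter?** SAP 13.4 runs the first analysis after the last WK16 visit, and secondary outcomes with later data are shown on what is available. A participant negative at WK18 with WK52 still to come is not yet an event, and becomes one, dated Day 126, once WK52 is in.

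**4. How large is the effect?** The plan gives no power, event count or hazard ratio for this endpoint, so there is no figure to reproduce. Its only precision figures concern EBA (0.2/√15 = 0.052; 1.96 × 0.0516 = 0.101, a half-width).

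Inputs: 15 per arm and weekly visits to WK16 (documents). Assumed, because the documents give none of them:
- q0, the share of D0 unconverted at WK16: 5% to 30%
- h, the true on-treatment hazard ratio: 1.5 or 2.0
- p, the chance, equal in both arms, that a remaining non-converter is negative at WK18 and confirmed at WK52: 0.3 to 0.9
- exponential conversion times

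Formulas: weekly hazard in D0 = -ln(q0)/16. Share unconverted at WK16 = q0 in D0 and q0^h in a delpazolid arm. Late events per 15 = 15 × q0 × p and 15 × q0^h × p.

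- q0 = 20%, h = 1.5, p = 0.6: D0 15 × 0.20 × 0.6 = 1.8; delpazolid 15 × 0.0894 × 0.6 = 0.8.
- q0 = 30%, h = 2, p = 0.9: D0 15 × 0.30 × 0.9 = 4.1; delpazolid 15 × 0.09 × 0.9 = 1.2.

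A two-arm Cox model (Efron ties) was fitted to the expected weekly counts, once with observation ended at WK16 and once open-ended:

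| q0 | h = 1.5: cut | h = 1.5: open (p 0.3 to 0.9) | h = 2.0: cut | h = 2.0: open (p 0.3 to 0.9) | Shift toward 1 |
|---|---|---|---|---|---|
| 5% | 1.497 | 1.493 to 1.486 | 1.991 | 1.988 to 1.983 | under 1% |
| 10% | 1.498 | 1.488 to 1.469 | 1.995 | 1.984 to 1.963 | at most 2% |
| 20% | 1.499 | 1.472 to 1.427 | 1.998 | 1.959 to 1.890 | 2-5% |
| 30% | 1.500 | 1.451 to 1.379 | 1.999 | 1.919 to 1.794 | 3-10% |

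Example: (1.998 - 1.890)/1.998 = 5.4%. The cut fit counted first negatives up to WK15, that is, those confirmed by WK16. Admitting a WK16 negative confirmed at WK18 adds on-treatment events under the same hazard ratio. Breslow ties lower both fits but leave the direction unchanged.

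Simulation of 15 versus 15 (800 runs per case, p = 0.6), median HR from cut to open: at q0 = 10%, 1.47 to 1.47 and 2.02 to 2.02; at q0 = 30%, 1.44 to 1.39 and 2.01 to 1.89. The median standard error of log HR was 0.38 to 0.43.

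Against that error: ln(1.998/1.890) = 0.056, and 0.056/0.4 = 0.14 standard errors. The largest case is ln(1.999/1.794) = 0.108, or 0.27 standard errors.

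**The case against.** The plan shows a 16-week intent. The Kaplan-Meier proportions are for time points during treatment, the Table 2.8 percentages stop at 16 weeks, and SAP 13.4 and 13.5 separate the 16-week analysis from endpoints needing later data. Events after week 16 cannot alter a Kaplan-Meier estimate at or before week 16. This stands, and it confines the exposure to the hazard ratios, the mean and late centiles. It does not close the gap, because none of these passages cuts each participant's data at week 16.

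Late events should also be few. Each needs negatives at both WK18 and WK52, Protocol 10.5.3 allows WK52 by telephone (no culture), and many WK52 cultures will be missing at the first lock. This also stands, and it argues for the lower values of p.

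Three stronger readings are tempting but unsupported:
- A reader might infer that late conversions are credited to delpazolid. The rule is the same in all five arms, and if delpazolid works most of these events fall in D0.
- A reader might infer a serious bias in dose selection. The shift is a fraction of a standard error in a secondary comparison with no stated power or threshold. Its direction depends on similar late conversion across arms.
- A reader might infer marked non-proportionality. That was not computed, and SAP 12.1 already plans Schoenfeld diagnostics and a fallback.

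Finally, a cut at week 16 alone does not restore time on treatment. Protocol 13.7 keeps participants who stop study drugs early on the assessment schedule, so conversions off treatment before week 16 would still count.

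**Conclusion.** The gap is real and the effect modest. The SAP rule conflicts with the protocol's time-on-treatment definition. Read literally, it scores conversions on non-study therapy as Cox events, and neither sensitivity definition removes them. Given equal late conversion across arms and exponential conversion, the hazard ratio moves toward 1 by under 1% to about 10% as the unconverted share of D0 at week 16 goes from 5% to 30%. That share is unknown. Even the largest shift is small against a standard error of log HR of about 0.4.

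The case for changing the text rests on an undefined observation period, a conflict between the two documents and an estimate that could differ between locks, not on large bias. Week-16 percentages, and any median reached by then, stand as planned.

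**What to change.** In SAP 11.4 and 12.1:
- State that the first negative timepoint must fall on or before the WK16 visit and that a WK18 culture may only confirm a WK16 negative. Also say what happens when a WK15 negative is followed by a WK16 visit with no evaluable result.
- Censor everyone else at their last evaluable culture on or before WK16, and apply this to the Cox model and to the hazard-ratio, mean and centile rows of Table 2.8.
- Use week 16 as the truncation time for restricted mean survival time.
- State how conversions after early discontinuation of study treatment are counted.
- Reconcile the protocol's time on treatment with the SAP's start at randomisation.

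This takes a few sentences and no new data. The cost is slightly fewer events.

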3.2. Efficacy Objectives

3.2.1. Primary Efficacy Objective:

To establish an exposure-response model for DZD, given over 16 weeks in combination with standard-dose BDQ, DLM and MXF, on the change in liquid culture MGIT time to positivity (TTP).

3.2.2. Secondary Efficacy Objectives:

- To assess dose and exposure-response relationships for DZD, based on secondary efficacy endpoints, including month-2
 culture status in liquid media and on solid media, and time to culture conversion in liquid and on solid media.
- To assess the relative efficacy of increasing DZD doses compared to the background regimen without DZD, based on primary and secondary efficacy endpoints.
- To assess the proportion of patients who suffer relapse within 12 months post randomization, out of those patients completing 16 weeks of therapy and achieving sustained sputum culture conversion, defined as two successive negative liquid media cultures at or before WK08, with no positives to follow until the week 16 visit.

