4.2. Randomization

Randomization will be implemented after all screening results are available for participants who have given informed consent and who have been found eligible for participation. Participants will be randomized by centralized allocation to a predefined list.

Participants will be allocated using the Internet-Based Randomization service system: RANDOMIZE.NET. Participant randomization will be stratified by bacterial load in sputum as measured by GeneXpert, cycle threshold (≥ 16, < 16), site (seven sites have been activated: The Aurum site, UCTLI, TASK Eden, Clinical HIV Research Unit (CHRU), KCRI/KIDH, the Ifakara site and the NIMR-MMRC site), and HIV status (positive, negative). Each site will have its own account and the allocation result will be generated by the web system immediately based on the minimization randomization algorithm. The minimization algorithm allocates the patient to the treatment arm with the lowest allocation proportion.

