4.3. Sample Size Determination

15 participants per arm with a total of 75 participants, and a wide range of DZD doses (from 0mg to 800mg BID) has been determined as an adequate sample size for population PK modelling, and for exposure response modelling to detect a clinically meaningful dose-dependent relationship.

Furthermore, the planned sample size of 15 participants per treatment group is in keeping with other trials of this type and accounts for the possibility of up to 3 drop-outs per group, which based on previous studies of this type conducted at these sites, represents a conservative estimate of the expected drop-out rate.

Previous Phase IIA (EBA) studies indicate that the between patient standard deviation of logCFU can be approximately 0.2. Therefore, assuming similar variability in this trial the expected standard errors of group mean EBA and corresponding width of 95% confidence intervals are 0.052 and 0.101 respectively for a group size of 15 and 0.063 and 0.124 respectively for a group size of 10.

This level of precision with a group size of 15 is considered adequate.

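### Time to culture conversion has no planned dose or exposure term, and its main Cox model adjusts for baseline TTP but not for HIV status, GeneXpert Ct stratum or site

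*SAP*

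**What the plan says.** SAP 3.2.2 lists two separate secondary objectives that bear on this endpoint. The first is "To assess dose and exposure-response relationships for DZD, based on secondary efficacy endpoints", and it names time to culture conversion among those endpoints. The second is the relative efficacy of the increasing doses against the regimen without DZD.

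SAP 12.1 gives the model: "A Cox regression model will be used to compare each arm with different DZD doses to the background regimen without DZD". On covariates it says: "The analysis will be adjusted for the baseline cultures using time to positivity (TTP) at the time of screening and enrolment". An open-ended list of demographic and clinical characteristics, which includes HIV status, smoking and alcohol, is added in sensitivity analyses. No significance level, power or multiplicity rule is stated for these contrasts.

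SAP 4.2 describes allocation: "Participant randomization will be stratified by bacterial load in sputum as measured by GeneXpert", with Ct split at 16, together with site (seven) and HIV status.

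Table shell 2.8 takes Arm 1 as reference and has one unadjusted and one adjusted hazard ratio row. Its footnote reads: "Analysis has been adjusted for: gender, age, race, BMI, HIV status, baseline culture (using time to positivity".

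SAP 10.2 tests linear, Emax and sigmoid Emax relations for AUC, Cmax and Cmin, but only against the decline in bacterial load estimated from TTP.

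**The concern.** The trial exists to choose a dose. If an objective asks how conversion depends on dose or exposure and the plan fits only four separate arm effects, nothing prespecified answers it. Any curve drawn afterwards through the four hazard ratios would be chosen with the data in view, in an open-label trial.

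The covariates raise a related issue. Factors used to balance allocation are normally carried into the main model, both because they are expected to be prognostic and so that the analysis matches the design. Here none of the three is in the main model. In addition, the text and the table shell point to different adjusted hazard ratios, so the principal result is not uniquely defined.

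**Working it through.** **1. The plan's own figure.** SAP 4.3 gives "15 participants per arm with a total of 75 participants" and a "between patient standard deviation of logCFU can be approximately 0.2". SE = 0.2/√15 = 0.0516 and 0.2/√10 = 0.0632, matching the stated 0.052 and 0.063. The stated 0.101 and 0.124 equal 1.96 × SE, which is the half-width. These figures concern logCFU and say nothing about the precision of a hazard ratio for conversion.

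**2. Objectives against analyses for time to conversion.**

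| Objective (SAP 3.2.2) | Planned analysis |
|---|---|
| Each dose against background | Cox contrasts, SAP 12.1 |
| Dose and exposure-response | None: section 10 models TTP only, and 12.1 has no dose or exposure term |

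**3. Covariates.**

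| Factor | In minimisation | Main Cox model (12.1) | Sensitivity (12.1) | Table 2.8 adjusted HR |
|---|---|---|---|---|
| Baseline TTP | no | yes | yes | yes |
| HIV status | yes | no | yes | yes |
| Ct stratum | yes | no | not named | no |
| Site | yes | no | not named | no |

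Table 2.8 has no row for the TTP-only model that 12.1 describes as the main one. Its footnote also leaves out smoking and alcohol, which 12.1 lists.

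**4. What a trend term would gain or lose.** The documents give no hazard ratio or conversion rate, so these are assumptions: two-sided 5%; HR 1.5 to 3 for top dose against control; and either everyone converts (15 + 15 = 30 events per contrast, 75 overall) or 24 and 60 events. The smaller set corresponds to 80% converting, or to the 3 drop-outs per arm in "accounts for the possibility of up to 3 drop-outs per group" with all 12 remaining patients converting.

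- One contrast: power = Φ(½√d · ln HR − 1.96).
- One-df trend with scores 0 to 4 (daily doses 0, 400, 800, 1200, 1600 mg are equally spaced): power = Φ(√D · cov(score, log-HR)/SD(score) − 1.96), with SD = √2.
  - Linear truth: cov/SD = (√2/4) ln HR = 0.354 ln HR.
  - Plateau (all active doses equal): cov = 2 ln HR − 2 × 0.8 ln HR = 0.4 ln HR, so cov/SD = 0.283 ln HR.

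At HR 2.5, ln HR = 0.916:
- contrast: ½ × 5.477 × 0.916 − 1.96 = 0.55, power 71%
- trend, linear truth: 8.660 × 0.354 × 0.916 − 1.96 = 0.85, power 80%
- trend, plateau: 8.660 × 0.283 × 0.916 − 1.96 = 0.28, power 61%

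| HR | Events | One contrast | Trend, linear truth | Trend, plateau |
|---|---|---|---|---|
| 1.5 | 30 / 75 | 19.8% | 23.6% | 16.7% |
| 2 | 30 / 75 | 47.5% | 56.4% | 39.7% |
| 2.5 | 30 / 75 | 70.9% | 80.1% | 61.2% |
| 3 | 30 / 75 | 85.3% | 92.0% | 76.8% |
| 2.5 | 24 / 60 | 61.2% | 70.9% | 51.9% |

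**5. What omitting a prognostic factor costs.** Simulation: 800 trials per cell, assumed control median 8 weeks, weekly visits, censoring at week 16, top-dose HR 2.5, one balanced binary factor, and no TTP in either model. Power for top dose against control:

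| Prognostic HR of factor | Adjusted (linear truth) | Omitted (linear truth) | Adjusted (plateau) | Omitted (plateau) |
|---|---|---|---|---|
| 1 | 60.5% | 61.0% | 60.4% | 59.6% |
| 1.5 | 60.0% | 57.9% | 59.3% | 57.1% |
| 2 | 61.6% | 55.0% | 58.9% | 52.3% |
| 3 | 56.8% | 42.6% | 58.9% | 42.4% |

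The loss runs from nil to about 14 points under linear truth, and up to 16.5 in the plateau runs. The simulation error on each figure is about √(0.6 × 0.4/800) = 1.7 points. These are upper figures, because the planned model already contains TTP.

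**The case against.** Much of the case for the plan stands.

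- **The contrasts are not the wrong analysis.** A reader might infer that the Cox model fails the trial's objectives. It answers the relative-efficacy objective directly, and exposure-response is prespecified for the primary endpoint. What is missing is an additional analysis.
- **The minimisation factors are not all ignored.** HIV status is in the sensitivity analyses and in the displayed adjusted hazard ratio. Baseline TTP measures the same bacterial load that Ct represents. It is nevertheless a partial stand-in: baseline cultures can be contaminated or give no result (SAP 11.1), whereas Ct is needed before allocation.
- **A linear trend is not clearly better.** Protocol section 5 says no reliable dose-response was seen in the EBA study. In Protocol 6.1.4 the smallest daily logCFU change was at 1200 mg QD (−0.019) and the largest at 400 mg BID (−0.053). Total daily dose also ignores that Arm 5 is dosed twice daily.
- **Bonferroni is not the comparator.** Against a corrected contrast (51% at HR 2.5 with 30 events) the trend looks far stronger, but the SAP plans no correction and reports confidence intervals. Four independent 5% tests would give 1 − 0.95⁴ = 18.5% family-wise error, or about 15.5% with the shared control. That is a reason to read the four hazard ratios as estimates.
- **The shells can be updated.** The SAP Appendix says so. Which adjusted hazard ratio is the main one is still an analysis decision that the text should settle.

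**Conclusion.** The point holds as a gap and an inconsistency. Three findings rest on the text alone: time to conversion has no analysis matching its dose and exposure-response objective; Ct stratum and site are named in no Cox model and HIV status is absent from the main one; and 12.1 and the Table 2.8 footnote disagree on the main adjusted hazard ratio.

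The size in power terms is conditional. At HR 2.5 with all patients converting, a trend gains about 9 points (80% against 71%) if log-HR is linear in dose and loses about 10 (61% against 71%) under a plateau. The documents do not rule out a plateau, so they do not support the claim that the planned contrasts lose power, or that a linear trend should replace them as the main model. The gain from Ct and HIV beyond TTP cannot be computed from the documents. For an assumed prognostic HR of 1 to 3 with no proxy in the model it runs from nil to about 14 points (16.5 in the plateau runs), and it should be smaller once TTP is included. The case for the change is a stated objective left unanswered and a main model that does not reflect the allocation, at low cost to correct.

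**What to change.** Amend the SAP before the 16-week analysis, after which SAP 13.4 says the sponsor and study staff are no longer blinded:

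1. Keep the four hazard ratios against Arm 1 as the relative-efficacy estimates.
2. In the main Cox model, adjust for baseline TTP, HIV status and Ct stratum (≥16, <16). Use site as a stratum or in a sensitivity analysis, collapsed where sparse: 75/7 is about 11 patients per site, and separate site terms would cost six parameters.
3. Add a prespecified supplementary Cox model with a one-df term in daily dose or model-derived AUC, plus an Emax-type alternative for a plateau. Dose is randomised and known for everyone. AUC reflects the schedule but is not randomised and depends on the day-14 sampling, so state how patients without it are handled.
4. Give Table 2.8 a row for the main model and a separate, labelled row for the sensitivity model, with footnotes that match 12.1.

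The cost is SAP wording, two extra parameters (HIV status and Ct stratum) in 75 patients, and one supplementary model with its alternative shape. Ct, HIV status and site are already recorded for randomisation, and AUC is already derived for section 10, so no new data are needed.
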